7.2.1 Primary Efficacy Variable

The primary efficacy variable is IOP change from baseline (follow up value minus baseline value) and the primary time period is 24 weeks (measurements for the primary analysis are designated for the following timepoints: Weeks 4, 12, and 24).

7.2.2 Secondary Efficacy Variables

Secondary efficacy variables include:

- Time to initial use of nonstudy IOP-lowering treatment (as determined by the investigator)
- Percentage of Bimatoprost SR and SLT eyes achieving $\geq 20\%$ reduction in IOP from baseline
- IOP changes from baseline at Weeks 8, 15, and 20

7.2.3 Other Efficacy Variables

7.3 Hypothesis and Methods of Analysis

In general, continuous variables will be summarized by descriptive statistics including sample size, mean, standard deviation, median, minimum, and maximum. Categorical variables will be summarized by frequency and percentage.

7.3.1 Primary Efficacy Analyses

The primary efficacy analysis will be performed for patients in the mITT population. The primary efficacy variable is IOP change from baseline and Weeks 4, 12, and 24 are the primary analysis timepoints.

The null and alternative hypotheses for the comparison between Bimatoprost SR 15 µg treated eyes and SLT treated eyes at each visit of Weeks 4, 12, and 24 are:

- Null hypothesis: the difference in mean IOP change from baseline between the Bimatoprost SR 15 µg and SLT eye (Bimatoprost SR minus SLT) is > 1.5 mm Hg.
- Alternative hypothesis: the difference in mean IOP change from baseline between the Bimatoprost SR 15 µg eye and SLT eye (Bimatoprost SR minus SLT) is ≤ 1.5 mm Hg.

IOP change from baseline will be analyzed using a mixed effect model for repeated measures (MMRM). The model will include IOP change from baseline as the response variable and treatment, visit, eye, baseline IOP, treatment-by-visit, treatment-by-baseline, treatment-by-eye, and visit-by-eyes interactions as covariates. Unstructured correlation for study visits and compound symmetry correlation for eyes will be used for repeated measures on the same patient; if the model fails to converge, multiple imputation (MI) will be implemented before MMRM.

The mean difference between the Bimatoprost SR 15 µg eyes and SLT eyes (Bimatoprost SR 15 µg minus SLT) in the mITT population and the corresponding 95% confidence interval (CI) will be constructed at each visit from MMRM analysis. The noninferiority comparison for Bimatoprost SR 15 µg versus SLT at Weeks 4, 12, and 24 is the primary analysis. If the upper limit of the 95% CI is ≤ 1.5 mm Hg at all 3 visits Bimatoprost SR 15 µg statistical noninferiority to SLT is considered demonstrated. In addition, Bimatoprost SR 15 µg is considered clinically noninferior to SLT if the upper limit of the 95% CI is ≤ 1.0 mm Hg at 2 out of the 3 visits of Weeks 4, 12, and 24.

As part of the sensitivity analysis for the primary efficacy analysis, a PP analysis using the same MMRM model as the one used in the primary efficacy analysis will be performed. The PP analysis will be based on the data from PP population.

Additionally, a by-visit analysis using an ANCOVA model will be conducted using the data from ITT population, where the between-eye correlation will be included in the same way as the MMRM model used for the primary analysis.

7.3.2 Secondary Efficacy Analyses

Superiority Test of Bimatoprost SR 15 µg Versus SLT

A superiority test of Bimatoprost SR versus SLT will be performed once noninferiority is demonstrated in the primary efficacy analysis. Superiority of Bimatoprost SR versus SLT is considered achieved if the upper limit of the 95% CI is < 0 mm Hg at Weeks 4, 12, and 24. The mITT population will be used.

Time to Initial Use of Nonstudy IOP-lowering Treatment (As Determined by the Investigator)

Time to initial use of nonstudy IOP-lowering treatment from the date of first treatment (Bimatoprost SR and SLT) associated with each eye will be estimated.

Additionally, for Bimatoprost SR, the time to initial use of nonstudy IOP-lowering treatment from the last injection and the time to initial use of nonstudy IOP-lowering treatment from the second injection will be analyzed similarly.

Percentage of Bimatoprost SR and SLT Eyes Achieving ≥ 20% Reduction in IOP

Number and percent of Bimatoprost SR and SLT eyes that have achieved a ≥ 20% reduction in IOP by visit in each eye will be summarized.

IOP Change from Baseline at Weeks 8, 15, and 20

Summary statistics will be tabulated for IOP change from baseline at Weeks 8, 15 and 20;

[REDACTED]

7.3.3 Other Efficacy Analyses

[REDACTED]

Approval Date: 27-Mar-2020

7.3.4 Safety Analyses

Safety analyses will be performed for patients in Stage 1 and in Stage 2 safety populations. The Medical Dictionary for Regulatory Activities (MedDRA) nomenclature will be used to code adverse events. Adverse events will be coded from the verbatim text into preferred term and system organ class (SOC). The number and percent of patients reporting treatment emergent adverse events will be tabulated based on the primary SOC and preferred terms. Summary tables will be generated for all adverse events regardless of causality as well as treatment-related adverse events for the entire study and by treatment cycle. Other safety variables include vital signs (blood pressure, pulse rate, and temperature) and pregnancy test results. Ocular safety will be evaluated through assessment of visual acuity and visual field, evaluation of macroscopic bulbar conjunctival hyperemia and iris color, assessment of endothelial cell density and corneal thickness, IOP measurement, and biomicroscopic and ophthalmoscopic examinations (including gonioscopy with Bimatoprost SR implant assessment, optic disc examination, and dilated fundus examination).

Ocular adverse events and safety variables will be summarized by Bimatoprost SR or SLT eye, and nonocular safety variables will be summarized by patient. A separate summary will be provided for safety events occurring after nonstudy IOP-lowering medication has been initiated.

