treatment regimen assigned at randomization. Patients who have received nonstudy IOP-lowering treatment in both eyes will not receive Bimatoprost SR administration or Sham Bimatoprost SR administration in either eye, and therefore do not need to attend the Bimatoprost SR (or Sham Bimatoprost SR) administration visits and immediate postadministration visits (ie, Bimatoprost SR Cycle 2 administration [Week 16], Cycle 2 Day 2 safety visit, and Cycle 2 Day 4 and Week 2 phone calls, and for Stage 1 patients only, Bimatoprost SR Cycle 3 administration [Week 32], Cycle 3 Day 2 safety visit, and Cycle 3 Day 4 and Week 2 phone calls).

Contact Lenses

Use of soft contact lenses within 3 days and use of rigid gas permeable or hard contact lenses within 1 week prior to a scheduled study visit or Administration Day, or use of contact lenses of any kind within 1 week following any Bimatoprost SR (or Sham) administration in either eye is prohibited.

Other Medications

The following medications (or classes of medications) and treatment procedures are not permitted as concurrent therapy during the study unless the patient has already received nonstudy IOP-lowering medication or treatment in both eyes:

- Subconjunctival, sub-Tenon's, intravitreal, or other ophthalmic injections of any medications in either eye
- Use of any topical ophthalmic medications (except as described above and in [Section 4.5.1](#)) in either eye
- Surgical (incisional and laser) procedures that are not related to study-specific Bimatoprost SR (or Sham) and SLT administration procedures in either eye; patients may exit the study early if an ophthalmic incisional procedure is required
- Oral, intramuscular, or intravenous corticosteroids from 2 months prior to the Baseline visit through study exit
- Use of bimatoprost for hypotrichosis during the study period in either eye
- Use of cyclosporine ophthalmic solution during the study period in either eye
- Systemic use of carbonic anhydrase inhibitor

- Any initiation of or alterations in systemic regimen of beta-blocker containing medications from 2 months prior to screening through the study exit
- Use of corticosteroids in either eye (except as described in [Section 4.5.1](#) for postoperative use) or systemically during the study or historical use prior to Baseline within:
 - 3 years: intraocular fluocinolone acetonide

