## 11.0 SAFETY ANALYSES

All safety analyses will be performed using the Safety Population. As indicated in [Section 6.5](#), safety data collected at Screening for eligibility assessment will not be analyzed.

Non-ocular safety assessments include: non-ocular adverse events (AEs), clinical laboratory, vital signs (blood pressure, pulse rate and temperature), and pregnancy test. Ocular safety will be evaluated through: ocular AEs, best corrected visual acuity, visual field examination, specular microscopy, macroscopic iris color assessment, macroscopic conjunctival hyperemia assessment, gonioscopy / angle assessment, biomicroscopy (using a slit lamp), lens assessment, optic disc examination, dilated ophthalmoscopy, pachymetry, and anterior segment-optical coherence tomography.

[REDACTED]

Unless otherwise stated, the last non-missing safety assessment before the SLT treatment (Day 1) will be used as the baseline for all analyses of that safety parameter.

Analysis study periods are defined as follows:

- **During the study:** Date of SLT treatment through Week 52/Exit visit/last study visit available.
- **Analysis Cycle 1:** SLT Treatment date (Day 1) through the second Bim SR implant date – 1. If the second Bim SR implant was not given to a patient, all safety assessments through Week52/Exit visit/last study visit available will be included in analysis cycle1.
- **Analysis Cycle 2:** Second Bim SR implant date through the third Bim SR implant date – 1. If the third Bim SR implant was not given to a patient, all safety assessments through Week52/Exit visit/last study visit available will be included in analysis cycle 2.
- **Analysis Cycle 3:** Third Bim SR implant date through Week 52/Exit visit/last study visit available. Note that only Stage 1 patients were eligible to receive third Bim SR implant.

All summaries will be based on the first treatment received in each eye (Bim SR or SLT), except one patient who received both SLT and Bim SR in the same eye (Safety assessment will be summarized in Bim SR). For non-ocular safety measures, overall summaries will be presented. For ocular safety assessments, summaries will be presented for the periods of during the study, Analysis Cycle 1, Analysis Cycle 2, and Analysis Cycle 3 as shown in Figure 11-1 below.

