- Any treatment related non-ocular TEAEs,
- Any serious non-ocular TEAEs, and
- Any non-ocular TEAEs leading to study discontinuation.

Additionally, a summary by SOC, PT, and severity will be provided for non-ocular TEAEs.

For patient eye incidences of treatment emergent ocular adverse events, overall and by period summaries will be provided for the following categories:

- Any ocular TEAEs by SOC and PT
- Any ocular TEAEs by SOC, PT, and severity
- Any treatment related ocular TEAEs by SOC and PT
- Any serious ocular TEAEs by SOC and PT
- Any ocular TEAEs leading to study discontinuation by SOC and PT
- Any ocular TEAEs within two days of study treatment by SOC and PT
  - i.e, Ocular TEAEs that occur within two days from the Bim SR treatment or Bim SR sham
- Any ocular TEAEs after two days of study treatment by SOC and PT
  - i.e, Ocular TEAEs that occur after two days from the Bim SR treatment or Bim SR sham to next Bim SR treatment or Bim SR sham
- SLT procedure related ocular TEAEs by SOC and PT
  - i.e, Ocular TEAEs that occur starting from Day 1, but before the first Bim SR treatment will be summarized.

- Any corneal TEAEs of interest by SOC and PT (Corneal AEs of interest will be identified separately prior to database lock.)
- Any anterior segment inflammation TEAEs of interest by SOC and PT (Anterior segment inflammation AEs will be identified separately prior to database lock.)

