### 11.3.4 Macroscopic Conjunctival Hyperemia

Severity assessment of hyperemia of both eyes is performed at Screening, Baseline, during Analysis Cycle 1 and during Analysis Cycle 2 for all patients and during Analysis Cycle 3. Conjunctival hyperemia severity in each eye is assessed as 0 (None), +0.5 (Trace), +1 (Mild), +2 (Moderate), +3 (Severe) or 'Not Evaluable'. These data will be summarized by eye using the worst severity of hyperemia observed by study period.

In addition, worst severity grade increase greater than 1 (worsening, i.e, a change from 0 to 2 and above, from 0.5 to 2 and above, or from 1 to 3 and above) in hyperemia from baseline will also be summarized for each eye by study period. If the worst severity grade during a period is less severe compared to baseline, it will be considered as 'no increase'.

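### Protocol 7.3.4 promises a separate summary of safety events after non-study IOP-lowering medication starts; the readable SAP text plans none, so those events cannot be isolated

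*Protocol*

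**What the plan says.** Protocol 7.3.4 sets two rules for ocular safety. The main tables are by eye: "Ocular adverse events and safety variables will be summarized by Bimatoprost SR or SLT eye". Adverse event tables are to be produced "for the entire study and by treatment cycle". It then adds a third element: "A separate summary will be provided for safety events occurring after nonstudy IOP-lowering medication has been initiated".

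SAP 11.0 defines four periods. The first, during the study, is: "Date of SLT treatment through Week 52/Exit visit/last study visit available". The other three are Analysis Cycles 1, 2 and 3, each ending at the next implant or, if there is none, at the end of follow-up. Data are assigned to the first treatment the eye received, with one named exception for a patient given both treatments in the same eye.

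For ocular TEAEs, SAP 11.1 states that "overall and by period summaries will be provided for the following categories" and then itemizes the tables. For hyperemia, SAP 11.3.4 says: "These data will be summarized by eye using the worst severity of hyperemia observed by study period".

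**The concern.** The SAP presents itself as the detailed elaboration of the protocol's analyses, but one pre-specified safety summary has no counterpart in its readable text. Comparing the safety of Bim SR with SLT is part of the study objective.

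Rescued patients stay under observation to Week 52 (Protocol 8.9 and 8.10), so post-rescue safety data will exist. Rescue is decided eye by eye (Protocol 4.5.2), so the two eyes of one patient can differ in exposure to non-study drops. Several ocular summaries use a worst or any-visit value, so a single post-rescue reading can set an eye's result. Without the promised summary, a reader of the tables cannot tell whether an event or a worst grade arose on study treatment alone or after another drug had been added.

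There is a further route after rescue in both eyes. Protocol 4.5.2 lists other ocular medications and procedures that "are not permitted as concurrent therapy during the study unless the patient has already received nonstudy IOP-lowering medication or treatment in both eyes". Their effects would enter the same by-eye tables.

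**Working it through.** No arithmetic decides this point and there is no plan figure to reproduce. The check is a side-by-side reading.

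1. **What is promised.** One separate summary of safety events, triggered by the start of non-study IOP-lowering medication (Protocol 7.3.4).

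2. **Where the SAP could deliver it.**
   - Periods (11.0): cut at implant dates and end of follow-up, never at rescue.
   - TEAE definitions (11.1): onset or worsening relative to study treatment or cycle administration; no cut at rescue.
   - Itemized ocular TEAE tables (11.1): by SOC and PT, severity, relatedness, seriousness, discontinuation, within or after two days of administration, SLT-procedure events, corneal events and anterior segment inflammation. None is post-rescue.
   - Visual acuity, hyperemia, endothelial cell density, pachymetry and biomicroscopy (11.3.2, 11.3.4 to 11.3.7): by visit, period or cycle; none splits at rescue.

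3. **Where the SAP does use rescue.** The mITT rule (6.1), the table of medication use (8.4.2), time to first non-study treatment (10.2), the by-visit ANCOVA (10.4) and setting post-rescue IOP to missing (16.1). None is a safety summary.

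4. **Whether the omission is declared.** The SAP says openly that vital signs and pregnancy tests, also named in Protocol 7.3.4, will not be analyzed (6.4, 11.2, 11.3.1). It says nothing comparable about the post-rescue summary, and the numbered changes in SAP Amendment 1 (19.1) do not mention it.

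5. **The effect in Analysis Cycle 1.**
   - Under Protocol 4.5.2, a Bim SR eye given non-study topical treatment before Week 16 receives a sham at Cycle 2. If both eyes have been treated, neither eye is administered anything.
   - There is then no second implant, so under SAP 11.0 everything to the last visit falls in Analysis Cycle 1.
   - For a patient followed to Week 52, that is at least 52 − 16 = 36 weeks of post-rescue observation reported in the same cycle as first-implant safety.
   - The same applies to any patient whose second implant was withheld under Amendment 3 and who was rescued later, with the post-rescue stretch running from rescue to Week 52.

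6. **What the missing table would change.** It would leave the main tables as they are, because Protocol 7.3.4 calls it separate and does not remove post-rescue events from the by-eye counts. It would supply the breakdown.

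7. **Size.** The shift in a between-eye event rate would be roughly (rescue rate in SLT eyes − rescue rate in Bim SR eyes) × (rate of that event caused by the rescue drug). The documents give neither term for this trial, so neither size nor sign can be computed.

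**The case against.** The strongest reply is that by-eye, whole-study counting is the protocol's own rule, so the SAP has not misattributed anything. That is correct. A reader might infer that the omission causes rescue effects to be charged to Bim SR or SLT. The documents do not support this: with the promised table in place, the main tables would be identical. What is lost is the means of separating the events.

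A second reply is that the summary may be specified elsewhere. Table specifications are in a separate document (SAP 4.0) that was not available. SAP 11.0 has a short redaction, and no text can be read under SAP 17.0. This also stands, so the claim is limited to the readable SAP text. Still, SAP 11.1 lists its ocular tables one by one and this one is not there.

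Third, there is partial protection. Treatment-related tables rest on recorded causality, and rescue use and timing are tabulated by eye. Endothelial cell density and corneal thickness are described by visit, so visits before rescue are unaffected. The all-causality tables and the worst-grade hyperemia summary do not have that protection.

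Fourth, three further inferences should be resisted.
- The phase 1/2 figure of 40% without rescue or a second treatment at Month 12 (Protocol 1.2.3) is not a rescue rate. It pools rescue with repeat implants across Generation 2 dose strengths. Protocol 1.3 says prior data suggested that most patients go an extended time without rescue.
- The promise concerns medication. Later surgery is covered only if it follows the start of such medication, and patients needing an incisional procedure may exit early (Protocol 4.5.2).
- Exclusion 19 shows that the protocol recognizes prostaglandin-related hyperemia, but it also removes patients with a history of the moderate or worse form. The class of rescue drug is not fixed. No passage links topical rescue to endothelial cell loss.

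**Conclusion.** The point holds as a mismatch between protocol and SAP with a real but unquantified consequence for reading the safety tables. A pre-specified safety summary is missing from the readable SAP text without explanation. Following that text would leave post-rescue events and worst grades mixed with those seen on study treatment alone, most clearly within Analysis Cycle 1.

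A reader might want to state a bias of some percentage points, or to say which eye is made to look worse. The documents support neither, since any such figure would come entirely from assumed rescue and event rates.

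The conclusion assumes that the separate table specifications, the redacted text in SAP 11.0 and any text under SAP 17.0 do not already contain the summary or a reason for dropping it. If they do, the point reduces to adding a cross-reference in SAP 11.1.

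**What to change.** 1. In SAP 11.1, add a summary by Bim SR or SLT eye of ocular TEAEs with onset on or after the first non-study IOP-lowering medication in that eye. This meets the commitment in Protocol 7.3.4. State the trigger exactly, because the protocol sentence refers to medication while SAP 16.1 covers medication or procedure.
2. Beside the all-data tables, add a supportive summary of ocular TEAEs and worst hyperemia restricted to data before that date. This goes beyond what the protocol promises. It needs a note that follow-up then differs between eyes and depends on IOP control, so it supplements the whole-study comparison and does not replace it.
3. If the sponsor intends to drop the summary, record and justify that in SAP 17.0.

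The cost is some SAP wording and a few extra tables. SAP 10.2 already derives time to first non-study IOP-lowering treatment for each eye, and SAP 8.4.2 identifies these medications by eye from the eCRF. No new data, visits or changes in patient management are needed.

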7.4 Subgroup Analyses

Subgroup analyses will be detailed in the Statistical Analysis Plan.

7.5 Sample Size Calculation

The sample size calculation is based on paired-eye differences using a normal approximation with a 2-sided significance level of 0.05, assuming that there is no difference in mean IOP

change from baseline between Bimatoprost SR eyes and SLT eyes and that change from baseline in IOP has a standard deviation of 4 mm Hg. A sample size of 144 patients will provide approximately 98% power in showing noninferiority in 3 out of 3 timepoints with a noninferiority margin of 1.5 mm Hg, and 90% power in showing noninferiority in 2 out of 3 timepoints with a noninferiority margin of 1.0 mm Hg, assuming that both the between-eyes and the within-patient correlation coefficients are 0.5.

Assuming a premature discontinuation rate of 10%, approximately 160 patients are to be enrolled into this study (including approximately 40 patients in Stage 1 and 120 patients in Stage 2).

7.6 Interim Analyses

No interim analyses are planned.

8. Study Visit Schedule and Procedures

Patients who complete all study treatments will have a minimum of 20 visits and 5 phone calls. The schedule includes the following:

- Screening (up to 28 days); Washout period of up to 42 days for both eyes; and Baseline visit (up to 3 days)
- SLT treatment (Day 1) and phone call (Day 2)
- Bimatoprost SR Cycle 1 administration (Day 4); Cycle 1 Day 2 safety visit; Cycle 1 Day 4 and Week 2 phone calls; and follow-up study visits at Weeks 4, 8, 12, and 15
- Bimatoprost SR Cycle 2 administration at Week 16; Cycle 2 Day 2 safety visit; Cycle 2 Day 4 and Week 2 phone calls; and follow-up study visits at Weeks 20, 24, 28, and 31

With implementation of Amendment 3, no new patients can be enrolled into the study and study treatment/retreatment of enrolled patients will not be permitted.

- Follow-up visits at Weeks 36, 40, 44, 47, and 52/Exit

Stage 1 patients had an additional 2 visits and 2 phone calls as follows:

- Bimatoprost SR Cycle 3 administration at Week 32; Cycle 3 Day 2 safety visit; Cycle 3 Day 4 and Week 2 phone calls

IOP evaluations will occur at Hour 0 (08:00 AM \pm 1 hour) in all patients. Selected patients at selected sites will have additional IOP measurements performed at Hour 2 (Hour 0 + 2 hours [\pm 30 minutes]) and Hour 8 (Hour 0 + 8 hours [\pm 30 minutes]).

The study visits should adhere as closely as possible to the schedule shown in [Table 2](#) through [Table 6](#).

